4.3 Discussion of Study Design

The efficacy parameters being evaluated (EASI, BSA, IGA, and PP-NRS) are widely used and well-recognized indicators of the disease state of AD. A randomized, double-blind, vehicle-controlled design is being employed to mitigate bias in the collection and analysis of efficacy data.

Although this is a first-in-human study, the study is being conducted in the target population because of the potential for differences in absorption of ATI-1777 through the skin of patients with AD compared with that of healthy volunteers.

Plasma samples will be collected to preliminarily assess PK using a sparse sampling approach. As ATI-1777 is a topical medication and the molecule is metabolically labile, it is expected to have only minimal or no systemic exposure.

The 2% w/w concentration was chosen based on nonclinical toxicity and PK studies in repeat-dose rat and minipig models, which showed a NOAEL of 300 mg/kg/day.

4.4 Stopping Rules

4.4.1 *Individual Patient Stopping Rules*

A patient will stop treatment with investigational agent if one or combination of the following occurs during the study:

- An infection which meets the criteria as a study medication-related SAE
- A deep venous thrombosis and/or pulmonary embolism
- Lymphoma
- Hy's law (see [Section 6.3.2.1](#))

Treatment with study medication should be temporarily interrupted in the event of severe AEs considered related to study medication, or in the event of one or more of the abnormal laboratory values in [Table 5](#).

4.4.2 *Study Stopping Rules*

The sponsor and ProPharma safety physician will meet regularly (every 4 weeks) and assess the ongoing safety of the study. Attention will be paid to the number of severe AEs and SAEs, with particular focus paid to the number of patients who meet individual patient stopping rules. PK data will be used in the assessment: events associated with high plasma levels will be considered of high significance.

If the study is stopped, a restart will not occur without agreement of the IRB and the sponsor's medical monitor.

4.5 *End of Study*

A patient is considered to have completed the study if he/she has completed all study visits.

The end of the study is defined as the date of the last visit or last procedure of the last patient in the study.

5 STUDY POPULATION

Prospective approval of protocol deviations to recruitment and enrollment criteria, also known as protocol waivers or exemptions, is not permitted.

5.1 Inclusion Criteria

Patients must meet the following criteria to be eligible for participation in the study:

1. Able to comprehend and willing to sign the IRB-approved ICF prior to administration of study-related procedures.
2. Male patients or non-pregnant, non-nursing female patients 18 to 65 years old, inclusive, at the time of informed consent.
3. Pregnancy and Contraception:
 - WOCPB (see [Section 6.3.3](#)), must have a negative serum pregnancy test at the Screening Visit, a negative urine pregnancy test immediately prior to the first application of study medication on Day 1, and a negative urine pregnancy test at each study visit thereafter.
 - Sexually active heterosexual women must agree to use the following throughout the screening period and for 30 days after last study drug application. WOCPB who are not sexually active at Baseline and become sexually active during the study must agree to follow the birth control measures listed below.
 - Agree to use 2 forms of highly effective contraception, including 1 physical barrier (condom or diaphragm) plus another highly effective method, such as adequate hormonal method (e.g., contraceptive implants, injectables, oral contraceptives) or nonhormonal methods (e.g., intrauterine device) or male partner who is surgically sterile (vasectomy).
 - Male patients with partners of childbearing potential may be enrolled if they are:
 - Documented to be surgically sterile (vasectomy), or
 - Using 2 adequate forms of highly effective contraception, 1 of which should be a physical barrier until 90 days after the last administration of study medication.
4. Have a diagnosis of AD fulfilling the specified diagnostic criteria of Hanifin and Rajka ([Hanifin and Rajka 1980](#)).
5. Have at least a 6-month history of AD prior to the Screening Visit, and no significant AD flares for the 4 weeks prior to the Screening Visit.
6. Have at least 1 lesion that measures at least 3 cm² at the Screening Visit and on Day 1 prior to the first dose of study medication. This lesion must be representative of the patient's disease state, but not located on the hands, feet, or genitalia.
7. Have a stable diagnosis of moderate or severe (IGA score 3 or 4) AD at the Screening Visit.
8. Have AD affecting 3% to 20% BSA (not including head [neck, scalp, face], palms of hands, soles of feet, groin, and genitalia) at the Screening Visit.

9. Willing to refrain from washing area of treatment or swimming for 6 hours after each study medication application.
10. Willing to refrain from excessive sun exposure (e.g., sunbathing and/or tanning salon visits) and to minimize sun exposure (e.g., wear sun protective clothing, hat) as much as possible.
11. Willing to refrain from use of moisturizers, emollients, and sunscreen on AD study treatment areas for duration of protocol therapy.
12. Willing to refrain from participating in strenuous exercise that would cause profuse sweating for a period of 6 hours after each study medication application.
13. Willing to return to the clinic, follow all study instructions, attend all study visits, and complete study procedures.
14. In good general health and free of any known disease state or physical condition that, in the investigator's opinion, might impair evaluation of the patient or that might expose the patient to an unacceptable risk by study participation.
15. Willing and capable of taking appropriate coronavirus disease 2019 (COVID-19) risk mitigation precautions (e.g., wearing a mask in public, adhering to social distancing, etc.) as recommended or required by local, state, or federal guidelines during participation in the study.

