4 STUDY PLAN

4.1 Overall Study Design and Plan

This is a first-in-human, randomized, double-blind, parallel-group, multicenter, vehicle-controlled study to evaluate the efficacy, safety, tolerability, and PK of ATI-1777 solution following twice-daily applications to target areas of male and female patients, aged 18 to 65 years, inclusive, with moderate or severe AD. All AD lesions in protocol allowed areas should be treated. The study will be conducted at approximately 15 sites in the (US).

The study will consist of a Screening Period of up to 30 days, a 4-week Treatment Period, and a 2-week follow-up period. The maximum total duration of the study for patients remaining in the study until their final follow-up assessment will be 73 days.

A study schematic is provided in [Figure 1](#) and a Schedule of Events is provided in [Table 1](#).

4.1.1 *Screening Period*

The investigator will obtain a signed ICF from the patient before any study procedures are performed. For further details regarding the informed consent process, see [Section 10.3](#). Patients will undergo screening evaluations within 30 days of Day 1 to determine study eligibility (see [Section 5](#)). All the results of the screening evaluations should be available at the time that patient eligibility is reconfirmed prior to dosing.

The investigator will maintain a screening log to record details of all participants screened and to confirm eligibility or record reasons for screening failure, as applicable. Certain procedures conducted as part of the participant's routine clinical management and obtained before signing of informed consent may be utilized for screening purposes provided the procedure meets the protocol-defined criteria and has been performed within the timeframe defined in the Schedule of Events ([Table 1](#)).

At the end of the Screening Period, participants meeting all inclusion and no exclusion criteria will enter the Treatment Period.

4.1.2 *Treatment Period*

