A total of approximately 50 patients who meet all the entry criteria will be randomized on Day 1 via an interactive voice/web response system (IXRS) to ATI-1777 or vehicle treatment in a 1:1 ratio. Patients will be stratified at randomization by severity of AD (moderate versus severe). The study is randomized and double-blinded with regard to ATI-1777 and vehicle in order to prevent bias in treatment allocation and in the assessment of treatment effect. The investigator, site personnel, the sponsor, and their representatives involved in monitoring and conducting the study, and the patients will be blinded to the study medication administered. See [Section 7.3](#) for further details on the

method of assigning patients to the treatment groups, and [Section 7.2](#) for details on access to the treatment codes in the event of emergency unblinding.

During the Treatment Period, patients will apply study drug (ATI-1777 topical solution 2.0% w/w or vehicle) twice daily for 28 days to target areas affected by AD. Patients will be trained by site personnel on how to appropriately apply the study medication. See [Section 7.4](#) for further details on the dose and administration of ATI-1777 and vehicle.

On Day 1 of the study, patients will apply drug in the clinic. The application site will be assessed for serious or severe local AEs prior to discharge from the clinic. Subjects will be informed to contact the site if a severe or serious event occurs. Subjects will be asked to pay particular attention to any events in the first 24 hours after drug administration.

During treatment, patients will attend weekly study visits. At the study visits, AE collection, physical examinations, clinical disease assessments (EASI, IGA, BSA, and PP-NRS), vital sign assessments, PK evaluations, and clinical laboratory evaluations will be performed as detailed in the Schedule of Events (Table 1). Patients will complete a daily diary recording their dose administration and PP-NRS itch score during the study.

For all study participants, blood samples will be collected for PK analysis according to the sparse sampling approach described in [Section 6.4](#).

Participants who discontinue study medication earlier than Day 28 will have an Early Termination (ET) Visit at the time of study medication discontinuation and will return for a PTFU Visit, 2 weeks (± 3 days) after the Day 28/ET Visit (see [Table 1](#)).

4.1.3 *Follow-up Period*

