16. History of a serious local skin infection (e.g., cellulitis, abscess) within 5 years of the Screening Visit.
17. Positive serological test for HIV (antibody), hepatitis C virus (antibody), hepatitis B surface antigen, or hepatitis B core antigen antibody.
18. Known significant exposure (close contact [<6 feet] for ≥ 15 minutes) to an individual with a confirmed diagnosis of COVID-19 at any time during the Screening Period.
19. Herpes zoster or cytomegalovirus infection that resolved less than 2 months prior to the Screening Visit. Patients with a history of frequent outbreaks of herpes simplex virus (defined as 4 or more outbreaks a year).
20. Clinically significant ECG findings such as, but not limited to, baseline mean QTcF >450 msec for males or >470 msec for females (use of the ECG algorithm is acceptable for this purpose).
21. Known allergy to any of the inactive ingredients in the study drug.
22. Female patients who are pregnant, nursing, or planning to become pregnant during the study.
23. Legal incapacity or limited legal capacity.
24. Major surgery within 3 months of the Screening Visit.
25. Any other condition that precludes adequate understanding, cooperation, and compliance with study procedures or any condition that could pose a risk to the patient's safety, as per the investigator's judgment.
26. Use of potent inhibitors of cytochrome P450 3A4 such as (but not limited to) clarithromycin, erythromycin, diltiazem, itraconazole, ketoconazole, ritonavir, verapamil, goldenseal, and grapefruit.

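### The contraception rule for women names screening and the 30 days after the last dose, but not the treatment period between them

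*Protocol*

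**What the plan says.** Protocol Section 5.1, criterion 3, sets the contraception requirement for women: "Sexually active heterosexual women must agree to use the following throughout the screening period and for 30 days after last study drug application". The same sentence stands in the Protocol Summary. The sentence after it deals with women of childbearing potential who are not sexually active at baseline: those who "become sexually active during the study must agree to follow the birth control measures listed below". The male limb of the criterion runs "until 90 days after the last administration of study medication".

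Section 4.1 divides the study into three periods: "The study will consist of a Screening Period of up to 30 days, a 4-week Treatment Period, and a 2-week follow-up period". Section 4.1.1 separates the first two: "At the end of the Screening Period, participants meeting all inclusion and no exclusion criteria will enter the Treatment Period". Section 4.1.2 places the dosing in the treatment period, with study drug applied "twice daily for 28 days to target areas affected by AD".

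**The concern.** The two periods that the sentence names lie on either side of dosing, and neither contains it. A woman who is sexually active at screening can therefore satisfy the criterion, as worded, without agreeing to contraception on any day that she applies the drug. That is the exposure the rule exists to cover.

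This matters for three reasons:

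- The study is first-in-human, and Section 1.1.5 states that reproductive toxicology has not yet been studied.
- The criterion defines what a woman must agree to before she can enter, and Section 5 allows no waivers of enrollment criteria. A site should not have to infer the main period.
- Negligible systemic exposure is an expectation from minipig data (Section 1.1.5). Section 1.2 makes systemic exposure one of the things the study is to examine, and chooses patients because absorption through diseased skin may differ from that in healthy volunteers.

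A smaller wording point is in the same sentence. It binds sexually active heterosexual women in general, so read literally it includes postmenopausal and surgically sterile women, whom Section 6.3.3 does not count as being of childbearing potential.

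**Working it through.** The plan gives no figure to reproduce. The check compares the periods named in the criterion with the periods of the study, and then looks for the missing duty elsewhere.

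**Day count.** Inputs are a screening period of at most 30 days (Section 4.1), 28 days of dosing (Section 4.1.2) and 30 days after the last application (Section 5.1, criterion 3). The last application is taken to be on Day 28.

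| Period | Study days | Length | Named in the criterion? |
|---|---|---|---|
| Screening | Day -30 to Day -1 | 30 | Yes |
| Treatment | Day 1 to Day 28 | 28 | No |
| After last application | Day 29 to Day 58 | 30 | Yes |

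- Full span: 30 + 28 + 30 = 88 days.
- Named: 30 + 30 = 60 days.
- Not named: 88 - 60 = 28 days, all of them dosing days.
- Applications on those days: 28 × 2 = 56 at most.
- With the ±2-day window on the Day 28 visit, dosing could last 26 to 30 days, which is 52 to 60 applications.

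**Search for the duty elsewhere.**

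- *Criterion 3, next sentence.* It does impose the measures during the study, but only on women of childbearing potential who were not sexually active at baseline. The gap is therefore confined to women already active at baseline.
- *Criterion 3, sub-bullet.* It lists acceptable methods and gives no dates.
- *Section 5.2, exclusion 22.* It excludes "Female patients who are pregnant, nursing, or planning to become pregnant during the study". This screens for intent and sets no contraception duty.
- *Section 5.4.1.* Study medication stops once pregnancy is confirmed.
- *Section 6.3.3.* It covers testing, reporting and follow-up of pregnancy.
- *Section 7.5 and Appendix 2.* They give lifestyle and application rules and do not mention contraception.
- *SAP.* It does not address contraception.

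**Is the omission deliberate?** Almost certainly not. The named periods bracket treatment, the next sentence reaches into the study, and the male limb runs without a break. The protocol also names the period when it means to, and for a lesser matter. Criterion 11 reads: "Willing to refrain from use of moisturizers, emollients, and sunscreen on AD study treatment areas for duration of protocol therapy".

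**The case against.** The best reply is that nobody would apply the sentence literally. On that reading a woman who becomes sexually active on Day 10 must use two methods, while one who was active at screening may stop on Day 1. No sensible site would run the study that way. Other controls also operate during dosing: pregnancy tests at the treatment visits with a negative result needed to continue, exclusion of women planning pregnancy, and withdrawal of drug on a positive test. The day count restates in numbers that one period is unnamed, and the point about postmenopausal or sterile women creates no hazard.

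Much of this stands. Intent is clear, the practical risk is small, and the count measures only the wording. The over-inclusive reference to women is a tidying matter.

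It does not remove the defect. The other controls screen for intent or detect a pregnancy after it has begun; none requires prevention while the drug is in use. Detection also has a limit. The SAP schedule shows urine tests on Days 1, 8, 15 and 28 and none on Day 42, and Protocol Section 6.3.2 likewise places them in the treatment period (Section 6.3.3 says every study visit). On that schedule a conception late in dosing could go untested on study.

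**Conclusion.** The criterion is wrong as written and should be corrected. For women already sexually active at baseline it omits the whole exposure period: 28 of 88 days under a full screening period and a last application on Day 28. This is a drafting error in a safety criterion, not a contested design decision, and it has no effect on sample size, power, alpha or any analysis.

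Three limits apply. That continuous cover was intended is an inference, though a strong one. The number of women affected cannot be derived from the documents. The consent form and the page between the reference list and Appendix 2 were not available, so it is not known whether patients were told to continue contraception during treatment. The finding concerns the wording of the criterion and alleges no lapse in consent.

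**What to change.** In criterion 3, in both the Protocol Summary and Section 5.1:

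1. Insert *throughout the treatment period* between the two periods now named, so that cover runs without a break from screening to 30 days after the last application (about Day 58 if the last dose is on Day 28).
2. Replace the general reference to women with sexually active heterosexual WOCBP, cross-referring to Section 6.3.3.
3. Check that the consent form states the same duty.

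The cost is one sentence in two places and a check of the consent form, with no added visit, test or patient.

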5.2 Exclusion Criteria

Patients with any of the following are excluded from the study:

1. Unstable course of AD (spontaneously improving or rapidly deteriorating) based on the patient history or as determined by the investigator during the Screening Period.
2. Refractory AD (i.e., AD that required frequent hospitalizations and/or frequent intravenous treatment for skin infections within the year before the Screening Visit).
3. AD of a severity (EASI >48) that the patient is not a candidate for a vehicle-controlled study.
4. Any signs or symptoms associated with AD therapy (e.g., history of anaphylaxis, hypersensitivity reactions, skin atrophy, striae, pigmentary changes) that, in the investigator's opinion, might impair evaluation of the AD or that exposes the patient to unacceptable risk by study participation.
5. Concomitant skin disease or clinically infected AD or presence of other skin disease in the area to be dosed that may interfere with study assessments.
6. Use of any of the following treatments within the indicated washout period prior to Day 1:
 - Phototherapy (ultraviolet A, ultraviolet B, or psoralen and ultraviolet A therapy) within 4 weeks prior to Day 1.
 - Systemic biologic immunosuppressant or immunomodulatory therapy (e.g., etanercept, alefacept, infliximab, dupilumab) within 12 weeks (or 5 half-lives of the product, whichever is longer) prior to Day 1.

- Non-biologic immunosuppressants (e.g., methotrexate, retinoids, calcineurin inhibitors, cyclosporine, hydroxycarbamide [hydroxyurea], azathioprine) within 4 weeks prior to Day 1.
- JAK inhibitors (systemic and topical) within 4 weeks prior to Day 1.
- Systemic corticosteroids within 2 weeks prior to Day 1 (intranasal, inhaled, and topical ocular corticosteroids are allowed).
- Cytostatic agents within 4 weeks prior to Day 1.
- Crisaborole within 2 weeks prior to Day 1.
- Systemic antibiotics within 30 days prior to Day 1.
- Topical treatments for AD (corticosteroids, calcineurin inhibitors, topical H1 and H2 antihistamines, topical antimicrobials, and other medicated topical agents) within 2 weeks prior to Day 1.
- Live attenuated vaccine treatment within 12 weeks prior to Day 1.
- Other investigational product within 30 days or 5 half-lives (whichever is longer) prior to Day 1.

7. Previous failure to respond to prior therapy with JAK inhibitors (systemic or topical), as determined by the investigator.
8. Current use of an oral H1 antihistamine (e.g., diphenhydramine, terfenadine) UNLESS the patient is on a stable dose for at least 14 days prior to the Screening Visit.
9. Medical marijuana unless the patient is on a stable dose for at least 14 days prior to the Screening Visit.
10. Clinically significant laboratory abnormalities at the Screening Visit that, in the opinion of the investigator, could affect interpretation of study data or the safety of the patient's participation in the study.
11. Clinical laboratory values:
 - White blood cell (WBC) count $<2 \times 10^9/L$
 - ANC $<1800/\mu L$
 - Platelet count $<130,000/\mu L$
 - Hemoglobin $<8g/dL$
 - AST or ALT $>2 \times ULN$
 - Lymphocyte count $<0.5 \times 10^9/L$
12. Investigator-assessed history of, or current physical findings of, severe, progressive or uncontrolled immunologic, hepatic, gastrointestinal, pulmonary, cardiovascular, genitourinary (renal), hematological, neurologic or cerebral disorders, infectious disease or coagulation disorders that, as determined by the investigator, could affect the safety of the patient's participation in the study or would preclude participation in and completion of study assessments.
13. History of, current, or suspected systemic or cutaneous malignancy and/or lymphoproliferative disease within the last 5 years, other than patients with a history of adequately treated and well healed and completely cleared nonmelanoma skin

cancers (i.e., basal or squamous cell carcinoma) or cervical carcinoma in situ treated successfully at least 1 year prior to the Screening Visit 1 with no evidence of disease.

14. Evidence of active, chronic, or latent infections at the time of enrollment or a systemic infection including but not limited to a history of treated infection (e.g., pneumonia, septicemia) within 3 months prior to Day 1.
15. Patient has a known active or history of incompletely treated or untreated active tuberculosis. Patients with a history of active tuberculosis must have documented adequate treatment verified by the investigator. Patients who demonstrate evidence of latent tuberculosis infection (positive QuantiFERON® Tuberculosis Gold Test) will only be allowed to participate in the study if there is documented evidence of a completed adequate treatment course for latent tuberculosis and if active tuberculosis is excluded per the investigator's judgment.
16. History of a serious local skin infection (e.g., cellulitis, abscess) within 5 years of the Screening Visit.
17. Positive serological test for HIV (antibody), hepatitis C virus (antibody), hepatitis B surface antigen, or hepatitis B core antigen antibody.
18. Known significant exposure (close contact [<6 feet] for ≥ 15 minutes) to an individual with a confirmed diagnosis of COVID-19 at any time during the Screening Period.
19. Herpes zoster or cytomegalovirus infection that resolved less than 2 months prior to the Screening Visit. Patients with a history of frequent outbreaks of herpes simplex virus (defined as 4 or more outbreaks a year).
20. Clinically significant ECG findings such as, but not limited to, baseline mean QTcF >450 msec for males or >470 msec for females (use of the ECG algorithm is acceptable for this purpose).
21. Known allergy to any of the inactive ingredients in the study drug.
22. Female patients who are pregnant, nursing, or planning to become pregnant during the study.
23. Legal incapacity or limited legal capacity.
24. Major surgery within 3 months of the Screening Visit.
25. Any other condition that precludes adequate understanding, cooperation, and compliance with study procedures or any condition that could pose a risk to the patient's safety, as per the investigator's judgment.
26. Use of potent inhibitors of cytochrome P450 3A4 such as (but not limited to) clarithromycin, erythromycin, diltiazem, itraconazole, ketoconazole, ritonavir, verapamil, goldenseal, and grapefruit.

